#### For vascular disease:

[figure not shown]
Radiological changes by PET-CT and/or MR imaging

Time to resolution as defined above

Preservation of remission within 12 months

Number of recurrent exacerbations within 12 months

PK, PD evaluations in serum and CSF

[figure not shown]

### 3 Investigational plan

#### 3.1 Study design

The study will be conducted as an exploratory open-label pilot trial. There will be only one treatment arm. The improvement will be evaluated in comparison to the findings recorded at the baseline.

Figure 3-1 Study design

Approximately 10 subjects aged 18 to 60 years, who sign an informed consent and meet all inclusion and exclusion criteria in the screening period will enter into the study. The first dose of canakinumab will be administered as 300 mg IV.

At the end of the first month, an analysis will be conducted to assess the complete, partial, and non-responders to canakinumab treatment by physician.

Partial responders will be able to take the 2nd canakinumab dose as 300 mg IV infusion at the first month then will continue the canakinumab treatment with 150 mg IV infusions at monthly intervals for 4 times. The complete responders will continue the canakinumab treatment with 150 mg IV infusions at monthly intervals for 5 times. Non-responder or deteriorating patients will be dropped from the study at the first month evaluations.

At month 6, the patients will be able to switch to SC injections or continue as IV infusions of 150 mg canakinumab for additional 6 monthly administrations. Non-responder or deteriorating patients will be dropped from the study at the first month evaluations.

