### **5.5.5 Permitted dose adjustments and interruptions of study treatment**

The first dose will be started as 300 mg IV.. At the end of the first month, an analysis will be conducted to assess the complete, partial, and non-responders to canakinumab treatment by physician.

Partial responders will be able take the 2nd canakinumab dose as 300 mg IV infusion at the first month then will continue the canakinumab treatment with 150 mg IV infusions at monthly intervals for 4 times. The complete responders will continue the canakinumab treatment with 150 mg IV infusions at monthly intervals for 5 times. Non-responder or deteriorating patients will be dropped from the study at the first month evaluations.

At the end of the 6th month the administration route can be switched to subcutaneous injection.

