#### **5.5.13 Study completion and post-study treatment**

Information on the date the subject last took drug, the subject's completion or discontinuation of the study and the reason for discontinuation of the study will be recorded on the Study Completion CRF page.

Visit	Screening ***	1***	2	3	4	5	6	7	8	9	10	11	12	13	14	15
Day	-7 to 0	0	7	14	30	60	90	120	150	180	210	240	270	300	330	360
Blood biochemistry		X		X	X			X	X	X	X	X				
Inflammatory markers	X	X	X	X	X	X	X	X	X	X	X	X	X	X	X	X
Urine Test	X	X	X	X	X	X	X	X	X	X	X	X	X	X	X	X
PK markers		X	X		X	X	X			X		X				X
PD samples		X	X		X	X	X			X		X				X
MR-Doppler Imaging (PET-CT when necessary)		X	X	X	X	X	X			X		X				X
(*)CSF Puncture	X			X	X		X									
Neurological evaluation		X	X	X	X	X	X	X	X	X	X	X	X	X	X	X
BDCA (BD Current Activity)	X	X	X	X	X	X	X	X	X	X	X	X	X	X	X	X
Adverse Events	X	X	X	X	X	X	X	X	X	X	X	X	X	X	X	X
VAS for symptoms	X	X	X	X	X	X	X	X	X	X	X	X	X	X	X	X
Efficacy Assessment					X		X			X						X
Attack Assessment	X	X	X	X	X	X	X	X	X	X	X	X	X	X	X	X
Steroid usage assessment	X	X	X	X	X	X	X	X	X	X	X	X	X	X	X	X
Physician&Patient Global Assessment		X	X	X	X	X	X	X	X	X	X	X	X	X	X	X
Drug Administration		X			X	X	X	X	X	X	X	X	X	X	X	X

\*Optional

\*\* PPD test could be used within 6 months before patient study entry

**\*\*\* If needed, in Patient's emergency situation, Screening and Visit 1 assessment could be combining by the physician decisions. There is no need to be repeated same test for each visit (screening and visit 1)**

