### 5.10.7 Pharmacokinetics

All blood samples will be taken by either direct venipuncture or an indwelling cannula inserted in a forearm vein. It is important to note that the volume of blood sampling will be adapted to the age of the child according to clinical practice at the investigator site. For each scheduled PK sample, 2 mL of blood will be drawn into a plain barrier tube to obtain 1 ml serum. The sample will be allowed to clot during 45 minutes at room temperature. The serum will be obtained by centrifugation at approximately 2500 g for 10 minutes. The sample will be split into two aliquots to be transferred into polypropylene screw-cap tubes. Serum tubes will be frozen within 90 min of venipuncture and kept at  $\leq -18^{\circ}\text{C}$  pending analysis. One of the two serum samples is to be kept at the study site as a backup while the other one will be shipped to the analytical center.

Time points for canakinumab PK sample collection at Visits:

- Day 0 (Visit 1)
- Day 7 (Visit 2)
- Day 30 (Visit 4); pre-dose
- Day 60 (Visit 5); pre-dose
- Day 90 (Visit 6) pre-dose
- Day 180(Visit 9) pre-dose
- Day 240(Visit 11) pre-dose
- Day 360 (Visit 15) pre-dose

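### Section 3.1 adds up to 12 canakinumab administrations but the assessment schedule marks 13, and section 5.1.1 contradicts sections 3.1, 3.2 and 5.5.5 on the partial responder's second dose

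*Combined protocol and SAP*

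**What the plan says.** Section 3.1 starts every patient on one 300 mg IV dose and classifies response at the end of month 1. After that:

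- Complete responders: "The complete responders will continue the canakinumab treatment with 150 mg IV infusions at monthly intervals for 5 times".
- Partial responders: "Partial responders will be able to take the 2nd canakinumab dose as 300 mg IV infusion at the first month", followed by four monthly 150 mg infusions.
- From month 6, both groups switch to SC injection or "continue as IV infusions of 150 mg canakinumab for additional 6 monthly administrations".

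Section 5.5.5 repeats the first-half plan. For partial responders it has "Partial responders will be able take the 2nd canakinumab dose as 300 mg IV infusion at the first month" and "then will continue the canakinumab treatment with 150 mg IV infusions at monthly intervals for 4 times". Section 3.2 also provides a second 300 mg dose for partial responders, but gives no dose counts. It says only that dosing is four-weekly until month 6 and through the following six months.

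Three other places bear on the same plan:

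- **Assessment schedule** (the table printed under section 5.5.13). The row "Drug Administration" is marked at Visit 1 (Day 0) and at each of Visits 4 to 15 (Days 30 to 360).
- **Section 5.10.7.** The PK sampling list includes "Day 180(Visit 9) pre-dose" and "Day 360 (Visit 15) pre-dose". The Day 360 pre-dose label appears again under section 5.10.7.2.2.
- **Section 5.1.1.** The dose goes down to 150 mg IV once the first dose has been given. No exception is made for partial responders.

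The interval is four-weekly in sections 3.2 and 5.5.4. It is monthly in sections 3.1, 5 (treatment table) and 5.5.5, and 30 days in the visit schedule.

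**The concern.** Two parts of the operative dosing text do not agree: how many administrations a patient who completes the year should receive, and how much a partial responder should receive at the second administration. Sites working from different sections would plan differently.

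The consequences lie in conduct and reporting:

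- **Deviations.** Section 5.8 requires departures in study drug administration to be recorded, and section 8.1 builds the per-protocol set on the absence of major deviations. Whether a Day 360 dose given or omitted, or a second dose of 150 mg or 300 mg in a partial responder, is a deviation depends on the section read.
- **Exposure.** The summary in section 8.3 can be computed from the doses actually given, but there is no single plan to read it against.
- **SAE reporting period.** Section 6.2.2 counts 30 days from the last administration. If that is Day 330, the period ends on Day 360 (330 + 30), the last scheduled visit. If it is Day 360, it ends on Day 390 (360 + 30), and the schedule has no visit after Day 360.
- **PK.** The pre-dose labels on Day 180 and Day 360 cannot both be right under section 3.1. If Day 180 were the undosed day, the planned dosing history before the Day 240 sample would also change.

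**Working it through.** **1. Count from section 3.1**

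| | First dose | Rest of first half | Second half | Total |
|---|---|---|---|---|
| Complete responder | 1 | 5 | 6 | 12 |
| Partial responder | 1 | 1 + 4 | 6 | 12 |

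**2. Count from the assessment schedule**

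The drug administration row and the day row both have 16 columns and line up. The marked days are 0, 30, 60, 90, 120, 150, 180, 210, 240, 270, 300, 330 and 360, so 1 + 12 = 13. Section 3.1 does not reproduce this figure.

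**3. Can section 3.1 be placed on the calendar so that both Day 180 and Day 360 are dosed?**

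The first six doses fall on Days 0, 30, 60, 90, 120 and 150. The last six can start at month 6 or at month 7:

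- Start at month 6: Days 180 to 330. Nothing is given on Day 360.
- Start at month 7: Days 210 to 360. Nothing is given on Day 180, and the gap from Day 150 is 210 − 150 = 60 days, although dosing is meant to be monthly.

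Neither placement doses both days, while the schedule and section 5.10.7 treat both as dosing days.

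**4. Does a strict four-week interval explain the 13?**

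Dosing every 28 days from Day 0 puts the 13th dose on Day 12 × 28 = 336. That is 360 − 336 = 24 days before the Day 360 visit, against the ±7-day visit window in section 5.7. The next dose, on Day 13 × 28 = 364, would be a 14th. This is a third pattern and does not reconcile the other two.

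**5. Size of the count discrepancy, per completer**

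| | 12 administrations | 13 administrations | Difference |
|---|---|---|---|
| Complete responder | 300 + 11 × 150 = 1950 mg | 300 + 12 × 150 = 2100 mg | 150/1950 = 7.7% |
| Partial responder, second dose 300 mg | 2 × 300 + 10 × 150 = 2100 mg | 2 × 300 + 11 × 150 = 2250 mg | 150/2100 = 7.1% |

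If all 10 patients completed, the plan would be 10 × 12 = 120 or 10 × 13 = 130 administrations. Both totals fall if non-responders leave at month 1.

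**6. Size of the second-dose discrepancy, partial responders only**

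| | Second dose 300 mg (3.1, 3.2, 5.5.5) | Second dose 150 mg (5.1.1) | Difference |
|---|---|---|---|
| 12 administrations | 2100 mg | 300 + 11 × 150 = 1950 mg | 150/2100 = 7.1% lower |
| 13 administrations | 2250 mg | 300 + 12 × 150 = 2100 mg | 150/2250 = 6.7% lower |

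**7. Primary endpoint**

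Response is assessed on Day 30 and determines the second dose. Only the Day 0 dose precedes it, and all sections agree on that dose. The endpoint is unaffected.

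**The case against.** On the count, section 3.2 runs the first phase until month 6. If month 6 is included, dosing on Days 0 to 180 is seven administrations, and six more on Days 210 to 360 give 7 + 6 = 13, which matches the schedule. The disagreement might then be a slip in one numeral. This shows how the two figures may have arisen, but it does not remove the contradiction. It needs six later first-half doses for complete responders where sections 3.1 and 5.5.5 say five, and five for partial responders where they say four.

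On the second dose, section 5.1.1 is a short statement within the product description. Section 5.5.5 is the place for dose adjustment and sets out the partial-responder case explicitly, so a reader may let the specific text qualify the general. That is reasonable, but nothing in the protocol says so, and section 5.1.1 is where the investigational treatment is defined. The wording elsewhere is also uneven: sections 3.1 and 5.5.5 permit the second 300 mg dose, while section 3.2 directs it. Under the permissive wording, 150 mg might not be a deviation at all, so the 7.1% and 6.7% figures apply to a partial responder who would otherwise receive 300 mg. This adds to what must be clarified.

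On weight, the study is exploratory with 10 patients, exposure is summarised descriptively, and no planned analysis compares actual with planned dose. This stands, and it limits the point to the clarity of the dosing plan. The mix of four-weekly and monthly is probably loose wording and would not merit a comment by itself.

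**Conclusion.** The point holds in both parts and should be corrected.

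- **Count.** Section 3.1 gives 12 administrations and the schedule gives 13, for both responder types. The difference is one 150 mg administration per completer.
- **Second dose.** Section 5.1.1 and sections 3.1, 3.2 and 5.5.5 differ by 150 mg, for partial responders only.

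The count rests on the text of section 3.1 and the marks in the schedule, supported by the pre-dose labels in section 5.10.7. The milligram totals assume that the patient completes the year and that every later dose is 150 mg, as the plan states. The figures of 120 and 130 further assume that all 10 patients complete. Figure 3-1 is not available in the text reviewed and was not relied on. The documents do not settle which count or which second dose is intended, and this review takes no position on that.

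**What to change.** Reconcile sections 3.1, 3.2, 5.1.1, 5.5.4 and 5.5.5, the assessment schedule and section 5.10.7 so that they give:

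- one number of administrations, with the study days on which they fall;
- one statement on the partial responder's second dose, including whether it is optional or required;
- one term for the dosing interval, used also in the section 5 treatment table.

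The sponsor's clinical team should make these decisions. The drug administration marks and the Day 180 and Day 360 pre-dose labels, including the repeat under section 5.10.7.2.2, should then follow them. The SAE reporting period in section 6.2.2 should be checked against the day chosen for the last dose.

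The cost is a protocol amendment to text and table, with the approvals that section 10.1 requires (sponsor, ethics committee and, where required, health authority). The reconciliation itself adds no visit, procedure or patient contact.

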### **3.2 Rationale of dose/regimen, route of administration and duration of treatment**

Canakinumab will be administered IV 300 mg initially. After the initial dose, complete responders will be given 150 mg IV infusions for every 4 weeks until month 6. A second canakinumab 300 mg IV dose will be used for patients with a partial response, and they will continue to receive 150 mg IV infusions for every 4 weeks until month 6.

Depending on the response in the first 6-month period, 150 mg canakinumab will be given as SC injections or IV infusions for every 4 weeks during the second 6-month period.

### **3.3 Rationale for choice of comparator**

There will be no active comparator.

### **3.4 Purpose and timing of interim analyses/design adaptations**

At the end of 1st month primary end point will be assessed by the physician. Complete / Partial / Non responders will be determined.

At 3rd and 6th months, there will be additional analyses to evaluate steroid tapering, prevention of disease exacerbation, and general disease activity by physician.

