### 5.4 Treatment blinding

This will be an open-label, single arm study.

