### **5.9.4 Steroid Tapering**

Prednisolone dosage should be 20 mg or less at baseline, and it should not be increased during the trial.

At the end of Day 30, complete responders begin to decrease the steroid doses. Tapering target will be 2,5 mg for every 2 weeks. At Day 120, patients expected to use prednisolone no more than 5 mg / day.

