### **8 Data analysis**

#### **8.1 Analysis sets**

Investigators will enter the information required by the protocol into the Novartis Case Report Forms (CRFs). Non-obvious errors or omissions will be entered on Data Query Forms, which will be returned to the investigational site for resolution.

The data from all centers will be pooled and summarized with respect to demographic and baseline characteristics and efficacy and safety observations. [REDACTED]

[REDACTED] Data will be presented for the complete intent-to-treat population (all subjects having taken at least one dose of study medication) as well as the per-protocol population (all subjects who completed the study without major protocol deviations). Safety data will be evaluated for the safety population (all subjects having taken at least one dose and who have at least one post-baseline assessment).

Data summaries will be presented.

This trial is an exploratory study, and it is not powered for a statistical analysis. The statistical analyses of the measurements will be performed when possible, and these analysis will be done by the investigators and an independent Contract Research Organization.

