## **8.4 Analysis of the primary variable(s)**

### **8.4.1 Variable(s)**

Percentage of complete responders.

Symptoms measured by VAS.

Percentage of patients achieved appropriate steroid tapering.

Changes of general disease activity measured by BDCAF.

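### The unblinded physician's Day 30 category is both the efficacy outcome and the treatment decision, so the response rate is at risk of bias, in a direction that depends on which response counts

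*Combined protocol and SAP*

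**What the plan says.** Section 3.4 gives the assessment to the physician: "At the end of 1st month primary end point will be assessed by the physician". Section 3.1 agrees: "At the end of the first month, an analysis will be conducted to assess the complete, partial, and non-responders to canakinumab treatment by physician". Section 5.4 states that "This will be an open-label, single arm study".

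The category has three consequences for the patient:
- **Non-response** (3.1): "Non-responder or deteriorating patients will be dropped from the study at the first month evaluations".
- **Partial response** (3.2): "A second canakinumab 300 mg IV dose will be used for patients with a partial response". Complete responders go to 150 mg.
- **Complete response** (5.9.4): "At the end of Day 30, complete responders begin to decrease the steroid doses".

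The assessment schedule places the efficacy assessment and drug administration at the same visit, Visit 4 (Day 30). Section 7.5 does not require an adjudication committee. On the statistical work, 8.1 says "these analysis will be done by the investigators and an independent Contract Research Organization".

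The first variable in 8.4.1 is "Percentage of complete responders". Section 8.4.2 sets the efficacy claim at a response of at least 50% in at least half the patients. Section 8.7 sets the sample at 10. Section 2.1 is broader than 8.4.1: its primary endpoint is met by improvement in any one listed item without deterioration.

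**The concern.** One person, who knows the treatment, makes one call that serves both as the efficacy outcome and as the decision on what the patient receives next. Someone who wants a borderline patient to stay on drug has a reason to prefer partial over non-response. The complete/partial boundary carries consequences too, in the next dose and the steroid taper.

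The written criteria leave room for these reasons to act:
- Neurologic partial response has no numeric cut-off.
- CSF enters every neurologic category, yet the schedule marks the puncture as optional.
- In vascular disease, a stable aneurysm or calf satisfies both complete and partial response.
- A vascular patient with VAS improved by at least 50% and CRP reduced by 20-49% fits no category in 2.1.
- Section 2.1 uses at least 50% for complete and 20-49% for partial. Section 5.9.1 uses more than 50% and 20-50%. A patient at exactly 50% is complete under one and partial under the other.

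At stake is the only efficacy claim the plan defines. With 10 patients, each label that crosses the boundary being counted moves the observed rate by 1/10, or 10 percentage points.

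**Working it through.** **Inputs from the plan.** N = 10 (8.7). The success rule in 8.4.2 is read as at least 5 of 10. The plan gives no null rate, error rate or power for this rule, so there is no figure of its own to reproduce. The intent-to-treat set in 8.1 is everyone with at least one dose. Dropped non-responders therefore stay in the Day 30 denominator, and only the labels can move the rate.

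**Assumed inputs.** The documents give no true response rates and no relabelling fractions. All such values below are illustrative.

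**Case 1: complete plus partial counts as response.** Let p be the true rate and m the share of true non-responders labelled partial. The observed rate is q = p + m(1 − p), and the chance of success is P(X ≥ 5) with X ~ Binomial(10, q). For example, p = 0.40 and m = 0.10 give q = 0.40 + 0.10 × 0.60 = 0.46.

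| True p | m = 0 | m = 0.10 | m = 0.20 | m = 0.30 |
|---|---|---|---|---|
| 0.30 | q 0.30: 0.150 | q 0.37: 0.294 | q 0.44: 0.470 | q 0.51: 0.647 |
| 0.40 | q 0.40: 0.367 | q 0.46: 0.522 | q 0.52: 0.671 | q 0.58: 0.798 |
| 0.50 | q 0.50: 0.623 | q 0.55: 0.738 | q 0.60: 0.834 | q 0.65: 0.905 |

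**Case 2: complete response only, as in 8.4.1.** Assume 40% true complete (c) and 30% true partial (r).
- Non-response relabelled partial: c does not change, so P(X ≥ 5) stays at 0.367 for every m.
- A share d of complete labelled partial: q = c(1 − d). For d = 0.10, q = 0.36 and P = 0.271. For d = 0.20, q = 0.32 and P = 0.187.
- A share u of partial labelled complete: q = c + u × r. For u = 0.10, q = 0.43 and P = 0.444. For u = 0.20, q = 0.46 and P = 0.522.

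The risk is one-directional in Case 1. In Case 2 it can go either way.

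**Scale.** The exact 95% confidence interval for 5 of 10 is 0.187 to 0.813, so sampling error alone is already wide.

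**The case against.** The categories are not free choice. Sections 2.1 and 5.9.1 tie them to MRI and CSF in neurologic disease, and to patient and physician VAS, CRP, aneurysm size and calf swelling in vascular disease. Section 7.1 requires full source verification of the data behind primary variables, and 7.3 requires audits of key efficacy data before lock. An independent CRO already shares the analysis. The study is a declared pilot, not powered for a statistical analysis.

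Most of this stands as mitigation. It does not close the gap. Source verification compares the CRF with the source record; it does not test whether the label follows from the components. The pilot status does not remove the claim rule in 8.4.2.

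A reader might infer more than the documents support, in three ways:
- **That the rate is biased.** The documents show a mechanism and an incentive, not bias that has occurred, and give no size for it. They say physician; that this is the treating physician is a reasonable inference.
- **That the 8.4.1 percentage is inflated.** Keeping a patient on drug by recording partial instead of non-response leaves the percentage of complete responders unchanged. Recording partial instead of complete to obtain the second 300 mg dose would lower it. The large increases in Case 1 apply only if partial responders count.
- **That a program could replace the physician's category in every patient.** Neurologic complete response refers to the patient's condition before the attack, and the schedule has no such measurement. Partial clinical improvement has no cut-off, no rule maps NBDS, modified EDSS or Rankin scores to a category, and CSF may be missing.

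**Conclusion.** The point holds as a risk of bias. An unblinded physician's category is both outcome and treatment decision, without adjudication or independent derivation. The risk is upward for complete plus partial, or for improvement in any item. Its direction is unknown for the percentage of complete responders.

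Under the assumed values, at a true 40%, moderate relabelling can take the chance of meeting the 5-of-10 rule from 0.37 to as much as 0.80 in the first case. In the second it can move it down to 0.19 or up to 0.52. These figures show sensitivity at N = 10 and do not estimate what will happen. It is a change worth making because the components are largely recorded already.

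**What to change.** In 3.4 and 8.4, state that the category used for analysis is derived by the CRO from the recorded baseline and Day 30 components. It is kept separate from the physician's category, which continues to guide care.

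- **Vascular patients:** derive it by program from patient and physician VAS, CRP, aneurysm size and calf swelling. First reconcile the cut-offs in 2.1 with those in 5.9.1. Fix in advance how mixed profiles and stable size are classified for analysis.
- **Neurologic patients:** derive only what the data allow, namely change in NBDS, modified EDSS, Rankin and MRI, and CSF where done. State a rule for missing CSF in advance, and report the result beside the physician's category.
- **Reporting:** cross-tabulate derived against physician category and list every disagreement. Have the CRO run the Day 30 primary analysis.
- **Endpoint:** reconcile 2.1, 8.4.1 and 8.4.2 on which response is primary.

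This needs no extra assessor, visit or procedure. It costs more than a short program, because the classification rules must be written before data are seen. Some patients' analysed category will differ from the one they were treated by. The derived category still contains physician-rated VAS and examination findings, so it limits discretion over the label without removing the bias.
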